5.3.2. Laboratory Evaluation

5.3.2.1. Clinical Laboratory Evaluation

The clinical laboratory evaluations including hematology and clinical chemistry will be collected before dosing, 60 minutes, 120 minutes and 240 minutes after dosing at dosing period.

• Hematology

Hematology include Hematocrit, Hemoglobin, RBC, MCV, MCH, MCH concentration, ANC, WBC, Neutrophils, Eosinophils, Basophils, Lymphocytes, Monocytes, and Platelet. ANC will be derived by the following formula:

$$\text{ANC} = \text{WBC} \left(\times 10^3 / \text{mm}^3 \right) \times \text{Neutrophils (\%)} \times 10$$

• Clinical Chemistry

Clinical Chemistry include creatinine, BUN, AST, ALT, ALP, total bilirubin, albumin, total protein, sodium, potassium, chloride, glucose, bicarbonate, calcium, magnesium, and phosphorus.

The results of clinical laboratory evaluations will be summarized using mean, standard deviation, median, minimum and maximum for each dose group and overall at each time point during

dosing period. Additionally, a within-subject change will be calculated as the post-baseline measurement minus the baseline measurement and summarized after dosing. Therefore, the change from baseline will also be summarized.

The abnormal laboratory result will be noted as [L] and [H] for lower and for higher than the reference ranges, respectively, which supplied by the local laboratories. It will be displayed in listing. Shift tables will be produced by the non-missing results to compare the baseline with post-injection.

Abnormal laboratory results will be listed in Table 03.3.1 and Table 03.3.2.

- Table 03.3.1: Listing for Abnormal Complete Blood Count Values, Safety Set
- Table 03.3.2: Listing for Abnormal Metabolic Panel Values, Safety Set
- Table 04.1: Summary of Complete Blood Count, Safety Set
- Table 04.2: Shift Table of Complete Blood Count, Safety Set
- Table 05.1: Summary of Metabolic Panel, Safety Set
- Table 05.2: Shift Table of Metabolic Panel, Safety Set
- Listing 08.1: Complete Blood Count Part 1, Safety Set
- Listing 08.2: Complete Blood Count Part 2, Safety Set
- Listing 08.3: Metabolic Panel Part 1, Safety Set
- Listing 08.4: Metabolic Panel Part 2, Safety Set
- Listing 08.5: Metabolic Panel Part 3, Safety Set

5.3.2.2. Other Laboratory Variables

Screening for pregnancy will be performed (serum or urine β -HCG at screening and serum and urine β -HCG before dosing on Day 1, for WoCBP only). A Detailed listing of all pregnancies will be provided.

Other laboratory variables collected are:

- **Coagulation studies of TT and aPTT**

Coagulation studies including Thrombin Time (TT) and Activated Partial Thromboplastin time (aPTT) will be measured before dosing, 60 minutes, 120 minutes and 240 minutes after dosing at dosing period.

- **Cardiac troponin I/Cardiac troponin T**

Cardiac troponin I/Cardiac troponin T will be measured before dosing and 240 minutes after dosing at dosing period.

The results of Coagulation studies and Cardiac troponin I/Cardiac troponin T will be summarized by the descriptive statistics (n, mean, standard deviation, median, minimum and maximum) for

each dose group and overall at each time point during dosing period. Also, the change from baseline will be summarized.

The abnormal laboratory result will be noted as [L] and [H] for lower and for higher than the reference ranges, respectively, which supplied by the local laboratories. It will be displayed in listing. Shift tables will be produced to compare the baseline results with post-injection. Abnormal laboratory results will be listed in Table 03.3.3, Table 03.3.4 and Table 03.3.5. The results of pregnancy tests will be shown in Listing.

- Table 03.3.3: Listing for Abnormal Coagulation Studies Values, Safety Set
- Table 03.3.4: Listing for Abnormal Cardiac Troponin I Values, Safety Set
- Table 03.3.5: Listing for Abnormal Cardiac Troponin T Values, Safety Set
- Table 06.1: Summary of Coagulation Studies, Safety Set
- Table 06.2: Shift Table of Coagulation Studies, Safety Set
- Table 07.1.1: Summary of Cardiac Troponin I, Safety Set
- Table 07.1.2: Summary of Cardiac Troponin T, Safety Set
- Table 07.2.1: Shift Table of Cardiac Troponin I, Safety Set
- Table 07.2.2: Shift Table of Cardiac Troponin T, Safety Set
- Listing 08.6: Coagulation Studies, Safety Set
- Listing 08.7.1: Cardiac Troponin I, Safety Set
- Listing 08.7.2: Cardiac Troponin T, Safety Set
- Listing 08.8: Pregnancy Test, Safety Set

5.3.3. Vital Signs

Vital signs (BP, body temperature, RR, and HR) will be recorded at screening, before injection, during injection and imaging (beginning approximately 5 minutes prior to and continuing until 10 minutes after injection), and 30, 60, and 120 minutes post-injection, in a standardized manner. Blood pressures (SBP and DBP) will be measured only at 5 time points for every 2 minutes within 10 minutes after injection. Body temperature will be only collected twice at 5 minutes and 10 minutes within 10 minutes after injection.

The results of vital signs will be summarized using mean, standard deviation, median, minimum and maximum for each dose group and overall at screening visit and each time point during dosing period. The baseline for the vital signs will be the last measurement before dosing. Also, the change from baseline of the vital signs will be calculated as the post-baseline measurement minus the baseline measurement and summarized after dosing.

- Table 08: Summary of Vital Signs, Safety Set

- Listing 08.9: Vital Signs, Safety Set

5.3.4. Pulse oximetry

SpO₂ will be assessed pre-injection, during injection and imaging (beginning approximately 5 minutes prior to and continuing until 10 minutes after), and at 30, 60, and 120 minutes post-injection.

The result of SpO₂ will be summarized using mean, standard deviation, median, minimum and maximum for each dose group and overall at each time point during dosing period. Also, the change from baseline of SpO₂ will be summarized after dosing.

- Table 11: Summary of Pulse Oximetry, Safety Set
- Listing 08.12: Pulse Oximetry, Safety Set

5.3.5. Physical Examination

At screening, a complete physical examination will be performed. A focused physical examination including skin and cardiopulmonary assessments will be performed before dosing and during dosing at the following time points after contrast injection: 30, 60, and 120 minutes post-injection. Each focused PE assessment will be scored as either normal or abnormal. The baseline will be the last assessments before dosing. Any changes with respect to the baseline will be recorded and assessed.

Number and percent of subjects with normal and abnormal skin and cardiopulmonary conditions in physical examination will be tabulated. Shift tables for all categories of non-missing physical examination results will be produced to compare baseline results with post-injection results.

Physical examination with abnormal findings will be provided in a listing. No statistical analyses will be performed.

- Table 09.1: Summary of Physical Examination, Safety Set
- Table 09.2: Shift Table of Physical Examination, Safety Set
- Listing 08.10.1: Physical Examination Part 1, Safety Set
- Listing 08.10.2: Physical Examination Part 2, Safety Set
- Listing 08.10.3: Physical Examination Abnormal Findings, Safety Set

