6.2 Primary Endpoint

Adverse event (AE) reporting and changes in physical examination findings, vital signs (VS), clinical laboratory evaluations, oxygen saturation, and electrocardiograms (ECGs).

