7.4.2 Inclusion Criteria

To be eligible for study entry subjects must satisfy all of the following inclusion criteria:

1. Male or female subjects 20 years of age or older
2. Ability to understand and the willingness to provide written informed consent
3. Suspected of having cardiac disease or undergoing evaluation of cardiac anatomy for congenital heart disease
4. Negative pregnancy test within 24 hours of the procedure if subject is a woman of childbearing potential (WoCBP)

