9.1.2.2.7 Physical Examination

At screening, a complete physical examination will be performed. A focused physical examination will be performed before dosing and during dosing at the following time points for each contrast injection: 30, 60, and 120 minutes post-injection. Any changes will be recorded and assessed. Each PE assessment will be scored as either normal or abnormal.

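### The physical examination tables in SAP 5.3.5 cannot separate a new or worsened cardiopulmonary finding from an unchanged one in a subject already abnormal at baseline

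*SAP*

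**What the plan says.** Protocol 6.2 (Primary Endpoint) lists, besides adverse event reporting, "changes in physical examination findings, vital signs (VS), clinical laboratory evaluations" and other safety measures. The endpoint component is therefore change in findings, not abnormality as such.

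Protocol 9.1.2.2.7 (Physical Examination) asks for a focused examination before dosing and at 30, 60 and 120 minutes after injection. It sets the scale: "Each PE assessment will be scored as either normal or abnormal". It also says: "Any changes will be recorded and assessed".

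SAP 5.3.5 keeps the two-level score for the focused examination: "Each focused PE assessment will be scored as either normal or abnormal". For baseline it says: "The baseline will be the last assessments before dosing". It repeats that changes against baseline are to be recorded and assessed. The planned output is:

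- Table 09.1: "Number and percent of subjects with normal and abnormal skin and cardiopulmonary conditions in physical examination will be tabulated".
- Table 09.2: "Shift tables for all categories of non-missing physical examination results will be produced to compare baseline results with post-injection results".
- Listings 08.10.1 to 08.10.3, the last of which shows abnormal findings.

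Protocol 7.4.2 (Inclusion Criteria) describes the population: "Suspected of having cardiac disease or undergoing evaluation of cardiac anatomy for congenital heart disease".

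**The concern.** A two-level shift shows change only when a subject crosses the line between normal and abnormal. Someone already abnormal before dosing cannot cross it in the adverse direction, whatever the later examination finds. Both documents say that changes from baseline are recorded, yet none of the named tables uses them.

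The limitation falls on the cardiopulmonary examination. Subjects enter with suspected cardiac disease or for evaluation of congenital heart disease, so some abnormal cardiopulmonary baselines are plausible. Protocol 9.1.2.2.2 names serious cardiopulmonary reactions among its warnings. What is at stake is whether the physical examination tables describe the stated endpoint component in those subjects.

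**Working it through.** The documents give no figure on this point, so the check is to trace what each table can show.

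**Step 1: the four cells of Table 09.2, per body system** (N = normal, A = abnormal)

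| Baseline to post-injection | What the cell can contain |
|---|---|
| N to N | no abnormality at either time |
| N to A | a new abnormality |
| A to N | a baseline abnormality no longer found |
| A to A | an unchanged baseline finding, a worsened one, or a further new one |

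Only the last cell mixes change with no change.

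**Step 2: three hypothetical records, cardiopulmonary system**

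- Normal before dosing, crackles at 30 minutes: N to A. The change is visible.
- Murmur before dosing, murmur plus crackles at 30 minutes: A to A. The change is not visible if heart and lungs share one score. If they were scored separately, the lungs would show N to A, but a second or worse finding in the already abnormal organ would still be A to A.
- Murmur before dosing, the same murmur at 30 minutes: A to A. Nothing changed, and the table is right.

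A new skin finding in a subject abnormal only on the cardiopulmonary part still shows as N to A, because SAP 5.3.5 tabulates skin separately.

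**Step 3: other safety measures in the SAP**

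- Laboratory values (5.3.2): change from baseline and shift.
- Vital signs (5.3.3) and SpO2 (5.3.4): change from baseline.
- ECG (5.3.6): numeric changes, and a shift on three interpretation levels.
- Physical examination (5.3.5): a two-level shift only.

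**Step 4: where else a masked finding would appear**

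- Protocol 9.1.2.2 counts unfavourable signs and exacerbations of existing conditions as adverse events. SAP 5.3.1 counts events that start or worsen after dosing as TEAEs and tabulates them by dose. A finding reported this way is not lost.
- Protocol 9.1.2.2 also exempts expected fluctuation of a pre-existing condition that is not a clinically significant worsening. An examination change judged to be of that kind would appear in the listings but in no table.

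**Step 5: size**

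The documents do not give the share p of subjects with an abnormal cardiopulmonary baseline. The following illustrates the mechanism and is not an estimate. Assume that k = 2 of the 12 subjects in a cohort have a new cardiopulmonary finding, independently of baseline status, with one score per subject.

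| Assumed p | Expected in N to A: k(1 − p) | Chance at least one is in A to A: 1 − (1 − p)² | Chance both are: p² |
|---|---|---|---|
| 20% | 2 × 0.80 = 1.6 | 1 − 0.64 = 36% | 4% |
| 35% | 2 × 0.65 = 1.3 | 1 − 0.4225 = 58% | 12% |
| 50% | 2 × 0.50 = 1.0 | 1 − 0.25 = 75% | 25% |

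One subject is 1/12, about 8 percentage points of a cohort. Both p and k are assumed. The figures describe Table 09.2 alone, not whether the finding is seen elsewhere.

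**The case against.** The strongest reply is that the safety output as a whole already covers this. Adverse events are recorded at the same 30, 60 and 120 minute points as the focused examination. New wheeze or crackles after injection would normally be reported as an event and reach the TEAE tables. Heart rate, respiratory rate, blood pressure, SpO2, ECG and troponin are summarised separately. The dosing stops in Protocol 7.5.1.2 do not rest on the physical examination tables. With about 36 subjects, a reader can also compare time points in the listings. The two-level score comes from the protocol, and the SAP follows it in a descriptive study without hypotheses.

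Most of this stands, and it confines the point to the physical examination tables. What it leaves is a change not judged to be an adverse event, and the lack of any tabulated count of the recorded changes.

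A reader might draw stronger conclusions, which the documents do not support:

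- That the plan miscounts, or reports a new finding as no change. SAP 5.3.5 gives the A to A cell no such label. The cell correctly reports the planned score but is not informative about change.
- That Table 09.1 wrongly attributes existing disease to the drug. Its post-dose percentages do include persisting findings, but Table 09.2 cross-classifies by baseline and separates them from normal-to-abnormal results. It also shows any difference between cohorts in abnormal baselines.
- That heart and lungs certainly share one score. This is the natural reading of the SAP wording, but the CRF and table shells are not available to confirm it.
- That abnormal baselines are common. Suspected cardiac disease is not the same as an abnormal examination, and Protocol 7.4.3 excludes chronic obstructive pulmonary disease, ejection fraction below 40% and unstable cardiopulmonary conditions.

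**Conclusion.** The point holds in a limited form. For a subject whose cardiopulmonary examination is abnormal before dosing, Tables 09.1 and 09.2 cannot tell a new or worsened cardiopulmonary finding from an unchanged one, although the endpoint component is change in findings. This follows from the two-level score and needs no assumption about frequency.

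How many subjects it would affect cannot be stated. That depends on the share abnormal at baseline, on how the body systems are scored, and on how many changes are not reported as adverse events. The documents give none of these.

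It does not follow that new cardiopulmonary findings escape the safety analysis. This is a cheap improvement of low priority.

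**What to change.** In SAP 5.3.5, derive for each post-dose focused examination a yes/no flag for a finding that is new or worsened against the last pre-dose examination. Base it on the changes already to be recorded, and set it separately for each body system as collected.

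Report the number and percentage of subjects with at least one such finding, by dose and overall, at any time and at 30, 60 and 120 minutes. Place this count beside Tables 09.1 and 09.2, which both stay, and mark the flagged findings in Listing 08.10.3.

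The cost is a short addition to the SAP, one further table, and medical coding of the listed findings as new, worsened or pre-existing for about 36 subjects. No additional examination is needed. The coding involves judgement, so the rule should be written down before database lock.

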5.3.6. Electrocardiograms (ECGs)

Standard 12-lead ECGs will be performed at screening, before dosing on Day 1, and at 10, 30, and 60 minutes post-injection. Safety assessments will be based on the results of the standard 12-lead ECGs. The ECG parameters include QTc, QT, and HR and ECG interpretation will be classified as either normal, abnormal but not clinically significant (NCS), or abnormal clinically significant (CS).

In addition, modified 12-lead ECG monitoring will be performed during imaging to prevent the ECG electrodes from affecting the accessibility of the optimal imaging windows of echocardiography. Imaging can be performed with a modified 12-lead ECG, by repositioning the V5-V6 leads upward. If any clinically significant ECG changes indicative of arrhythmia or S-T segment change are identified within 10 minutes after dosing from the modified 12-lead ECG monitoring, an additional standard 12-lead ECG examination will be performed subsequently when the earliest ECG change occurs.

The descriptive statistics (n, mean, standard deviation, median, minimum, and maximum) of the ECG parameters at screening visit and each time point during dosing period including changes from baseline will be summarized and presented by each dose group and overall. The baseline will be the last measurements before dosing.

Number and percent of subjects with normal, abnormal, NCS and abnormal, CS results for the 12-lead ECG interpretation will be tabulated by each dosing group and overall. A shift table showing the changes of non-missing results in normal, abnormal, NCS and abnormal, CS from baseline to each post-baseline measurement will be displayed.

- Table 10.1: Summary of 12-Lead ECG Parameters, Safety Set
- Table 10.2: Summary of 12-Lead ECG Interpretation, Safety Set
- Table 10.3: Shift Table of 12-Lead ECG Interpretation, Safety Set
- Listing 08.11: 12-Lead ECG Test, Safety Set

5.4. Secondary Endpoints Analysis

5.4.1. Secondary Efficacy Endpoints

5.4.1.1. Definition of endpoints

- The percentage of subjects with moderate or complete LVO, defined by an LVO grade of 2 (moderate) or 3 (complete), as assessed by the blinded central reader(s);
- The percentage of subjects with complete LVO, defined by an LVO grade of 3 (complete), as assessed by the blinded central reader(s);
- The change from baseline on the LVEBD score, defined using a standard 12-segment model, as assessed by the blinded central reader(s). The LV endocardium of the 4- or 2-chamber apical views are divided into 6 segments, with 2 basal, mid-, and apical segments in each view. For each segment, LVEBD is graded as follows: 0 = inadequate border (border not visible); 1 = sufficient (border barely visible); 2 = good (border clearly visible). A total delineation score (0-24) is obtained by adding the scores from the 6 individual segments in each of the 2 views.
- The changes from baseline on LVEBD score of subjects with suboptimal LVEBD at baseline, as defined by 2 or more contiguous segments of 6 segments that cannot be

visualized reliably in either the apical 4- and/or the 2-chamber view, as assessed by the blinded central reader(s);

- The duration of clinically useful contrast calculated by measuring the time between the disappearance of shadowing effect (useful effect starts) and the time when moderate or full LV enhancement and contrast enhancement are no longer adequate (useful effect ends), as assessed by the blinded central reader(s).

5.4.1.2. Main analytical approach

- LVO Grade

A pair of apical 4-chamber and 2-chamber view images in each of the pre-injection and post-injection imaging sessions will be subjected to LVO grade assessment by central reading.

The highest LVO Grade among the pair of apical 4-chamber and 2-chamber view images of pre-injection and post-injection will be summarized and presented by each dose group and overall. When the LVO grades of both apical 4-chamber and 2-chamber view images are the same, the LVO grade of the apical 4-chamber view image will be used.

The following descriptive statistics will be summarized and presented:

- Number and percentage of subjects in each LVO Grade.
- Number and percentage of subjects with moderate or complete LVO.

In addition, the bar chart for Cumulative Percent of LVO Grade will be presented by pre-dose and post-dose groups in each cohort and overall.

Two LVO grades obtained for each session along with the corresponding times of images used will be listed.

- Table 12.1.1: Summary of LVO Grade, Full Analysis Set
- Figure 12.1.2: Cumulative Percent of LVO Grade, Full Analysis Set
- Table 12.2.1: Summary of LVO Grade, Per Protocol Set
- Figure 12.2.2: Cumulative Percent of LVO Grade, Per Protocol Set
- Listing 06.1: Image Evaluation - LVO Grade, Safety Set

- LVEBD Score

The descriptive statistics (n, mean, standard deviation, median, minimum, maximum, and 95% CI) of LVEBD score for pre-injection, post-injection and the change from baseline will be summarized and presented by each dose group and overall. LVEBD scores for subjects with suboptimal LVEBD at baseline (as defined by 2 or more contiguous segments of 6 segments that cannot be visualized reliably in either the apical 4- and/or the 2-chamber view) will also be summarized.

Moreover, the boxplots of the LVEBD score for pre-injection, post-injection and the change of LVEBD score will be presented by each cohort and overall.

Likewise, for subjects with suboptimal LVEBD at Baseline (as defined by 2 or more contiguous segments of 6 segments that cannot be visualized reliably in either the apical 4- and/or the 2-chamber view), the boxplots of the LVEBD Score for pre-injection, post-injection and the change of LVEBD score will be presented by each cohort and overall.

- Table 13.1.1.1: Summary of LVEBD Score, Full Analysis Set
- Figure 13.1.1.2: LVEBD Score, Full Analysis Set
- Figure 13.1.1.3: Change of LVEBD Score, Full Analysis Set
- Table 13.1.2.1: Summary of LVEBD Score, Per Protocol Set
- Figure 13.1.2.2: LVEBD Score, Per Protocol Set
- Figure 13.1.2.3: Change of LVEBD Score, Per Protocol Set
- Table 13.2.1.1: Summary of LVEBD Score for Subjects with Suboptimal LVEBD at Baseline (as defined by 2 or more contiguous segments of 6 segments that cannot be visualized reliably in either the apical 4- and/or the 2-chamber view), Full Analysis Set
- Figure 13.2.1.2: LVEBD Score for Subjects with Suboptimal LVEBD at Baseline (as defined by 2 or more contiguous segments of 6 segments that cannot be visualized reliably in either the apical 4- and/or the 2-chamber view), Full Analysis Set
- Figure 13.2.1.3: LVEBD Score for Subjects with Suboptimal LVEBD at Baseline (as defined by 2 or more contiguous segments of 6 segments that cannot be visualized reliably in either the apical 4- and/or the 2-chamber view), Full Analysis Set
- Table 13.2.2.1: Summary of LVEBD Score for Subjects with Suboptimal LVEBD at Baseline (as defined by 2 or more contiguous segments of 6 segments that cannot be visualized reliably in either the apical 4- and/or the 2-chamber view), Per Protocol Set
- Figure 13.2.2.2: LVEBD Score for Subjects with Suboptimal LVEBD at Baseline (as defined by 2 or more contiguous segments of 6 segments that cannot be visualized reliably in either the apical 4- and/or the 2-chamber view), Per Protocol Set
- Figure 13.2.2.3: LVEBD Score for Subjects with Suboptimal LVEBD at Baseline (as defined by 2 or more contiguous segments of 6 segments that cannot be visualized reliably in either the apical 4- and/or the 2-chamber view), Per Protocol Set
- Listing 06.2: Image Evaluation - LVEBD Score, Safety Set
- Duration of Clinically Useful Contrast Enhancement

The duration of clinically useful contrast enhancement is the number of minutes between start time point and end time point of useful contrast imaging, rounded to one decimal place.

The formula for duration calculation is as below.

Duration (Minutes)=(End Time (hh:mm:ss) of Useful Contrast Imaging - Start Time (hh:mm:ss) of Useful Contrast Imaging)/60, rounded to one decimal place.

The descriptive statistics (n, mean, standard deviation, median, minimum, maximum, and 95% CI) of the duration of clinically useful contrast enhancement will be presented by each dose group and overall. The unit of duration is minute.

Furthermore, the boxplots of duration of clinically useful contrast enhancement will be presented by each cohort and overall.

- Table 14.1.1: Summary of Duration of Clinically Useful Contrast Enhancement, Full Analysis Set
- Figure 14.1.2: Duration of Clinically Useful Contrast Enhancement, Full Analysis Set
- Table 14.2.1: Summary of Duration of Clinically Useful Contrast Enhancement, Per Protocol Set
- Figure 14.2.2: Duration of Clinically Useful Contrast Enhancement, Per Protocol Set
- Listing 06.3: Image Evaluation - Duration of Clinically Useful Contrast Enhancement, Safety Set

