10.3 Demographic and Other Baseline Characteristics

Demographic and baseline characteristic data will be summarized for each cohort and overall. Descriptive statistics (N, mean, standard deviation, median, minimum, and maximum) will be presented for continuous variables and the number and percentage of subjects in each category will be presented for categorical variables. No formal testing of demographic or baseline characteristics will be performed. The impact of any imbalances in demographics or baseline characteristic variables on treatment effect may be investigated in exploratory analyses on select efficacy or safety variables; such analyses will be documented in the statistical analysis plan, if applicable.

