10.6 Methods of Analysis

The safety and efficacy variables of each dose of NH002 will be presented using descriptive statistics. A series of selection rules based on efficacy and safety will be applied to determine the maximum tolerated dose. If no single NH002 dose shows a clear benefit in safety or efficacy, the lowest dose of NH002 will be selected.

Secondary endpoints will be summarized by descriptive statistics. Graphical presentations of the data will be provided, where appropriate.

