10.8 Determination of Sample Size

Each of the expected 36 completed subjects will receive 1 dose of NH002 (with 12 subjects per NH002 cohort). As this is a dose finding study, a formal sample size calculation was not required. The number of subjects dosed within each cohort is based on safety, with the objective of exposing the lowest possible number of subjects to the investigational agent, while still being able to assess safety.

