1.2. Study Design

This is a phase 1, multicenter, open-label clinical study to evaluate the safety and tolerability of 3 ascending doses of NH002. Up to 36 eligible subjects will be enrolled with sequential allocation to 1 of 3 cohorts with the following intravenous (IV) doses of NH002: 2.5 μ l/kg, 5.0 μ l/kg, or 10.0 μ l/kg. Each patient will undergo an unenhanced ultrasound examination and a NH002 contrast-enhanced examination on the same day at Day 1. Subjects will remain at the clinical site for 240 minutes of observation after NH002 administration.

All AEs will be evaluated during the successive groups of subjects, per dose level. In general, enrollment will be halted and safety data reviewed for termination or continuation with the occurrence of any serious adverse event (SAE) considered at least possibly related to study agent administration (in any 1 subject) or the occurrence of clinically significant toxicity listed in the study protocol in 30% of subjects (within any 1 of the 3 dose levels). See Section 7.5.1.2 in the study protocol for details on stopping criteria for dosing for this trial.

There will be a screening period (28 days before NH002 administration), a dosing period (during Day 1) which will include a single dose administration of NH002, and a 7-day follow-up period for each cohort. Continuous echocardiographic imaging will be performed at specified time points before, during, and after dose administration. The contrast agent will be prepared and administered by designated pharmacy technician(s), study nurse(s), sonographer, or radiologist. Subjects will be observed at a clinical site for at least 240 minutes (i.e., 4 hours) and evaluated for AEs. Subjects will be contacted by phone after the end of treatment at 72 hours (i.e., Day 4 [+3]) and at Day 7 (+3), for a follow-up safety assessment. Any drug-related AE or SAE will be followed until resolution.

High ultrasound mechanical index (MI) values may cause microsphere cavitation or rupture and lead to ventricular arrhythmias. Additionally, end-systolic triggering with high MIs has been reported to cause ventricular arrhythmias. The safety of NH002 at MIs greater than 0.8 will not be evaluated.

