1.3. Randomization

This is a phase 1 dose ascending study without the use of an active control as well as a placebo control. No dose or treatment randomization is applicable.

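### LVEBD change is presented by dose without allowing for pre-injection score, in sequential non-randomised cohorts; an exploratory adjusted model would reduce, though not remove, the resulting confounding

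*SAP*

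**What the plan says.** SAP 5.4.1.2 lists for LVEBD "The descriptive statistics (n, mean, standard deviation, median, minimum, maximum, and 95% CI) of LVEBD score for pre-injection, post-injection and the change from baseline", by dose group and overall. Boxplots and a separate summary for subjects with a suboptimal baseline are added. No model, covariate or between-dose contrast is specified.

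On allocation, SAP 1.2 states "Up to 36 eligible subjects will be enrolled with sequential allocation to 1 of 3 cohorts" and SAP 1.3 states "No dose or treatment randomization is applicable". Protocol 10.8 gives the cohort size, "with 12 subjects per NH002 cohort".

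Two protocol passages bear on how the summaries will be used. Protocol 10.6 applies selection rules that draw on efficacy as well as safety and sets a default: "If no single NH002 dose shows a clear benefit in safety or efficacy, the lowest dose of NH002 will be selected". Protocol 10.3 offers an option, to be documented in the SAP if applicable: "The impact of any imbalances in demographics or baseline characteristic variables on treatment effect may be investigated in exploratory analyses". The SAP documents no such analysis. Protocol 10.1 assigns the dose selection strategy to the SAP, which sets none out, so the weight that LVEBD will carry is not stated.

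**The concern.** LVEBD is the sum of 12 segments scored 0 to 2, so the largest possible gain is 24 minus the pre-injection score. Unless change is unrelated to the starting value, a cohort with poorer unenhanced images will show a larger mean gain even if dose has no effect.

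Randomisation would make such a difference a matter of chance alone. Here the cohorts are recruited in sequence, so drift in site mix, referral pattern or case mix can add a systematic component. With 12 per cohort, chance is already large.

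A reader asked whether one dose shows a clear benefit would have three separate intervals for raw change. That is a noisier and more confounded basis than the data permit, because the main predictor of change, the pre-injection score, is already measured on every imaged subject.

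**Working it through.** **Nothing to reproduce.** Protocol 10.8 says "As this is a dose finding study, a formal sample size calculation was not required", and SAP section 2 marks hypotheses as not applicable. There is no alpha, power, effect size or SD. The only arithmetic in the documents is consistent: 3 × 12 = 36 subjects and 12 × 2 = 24 points.

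**Inputs.** From the documents: three cohorts of 12, a score range of 0-24, and unadjusted change by dose. Assumed, because the documents give none: pre-injection mean 14, SD 5 (range 3 to 6), post-injection mean 22, residual SD 2, and slope b of post on pre of 0.2 to 0.8.

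**Step 1, algebra without the cap.** With no dose effect, expected change is a constant plus (b − 1) × pre-injection score. A cohort whose pre-injection mean is lower by d shows a spurious extra gain of (1 − b) × d. For d = 4 this is 4, 3, 2, 1 and 0 points at b = 0, 0.25, 0.5, 0.75 and 1.

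**Step 2, is d = 4 plausible?** By chance alone, the 95% limits for the difference between two cohort means are ±1.96 × SD × √(2/12). This gives ±2.4 points at SD 3, ±4.0 at SD 5 and ±4.8 at SD 6. Systematic drift would come on top.

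**Step 3, simulation with the cap.** 6,000 runs per setting, no dose effect, scores rounded and clipped to 0-24, baseline SD 5. The bias columns have the top-dose cohort starting 4 points lower. The SE columns have no systematic imbalance.

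| Slope b | Bias, raw change | Bias, post score | Bias, adjusted | SE, raw change | SE, post score | SE, adjusted |
|---|---|---|---|---|---|---|
| 0.2 | 3.2 | −0.7 | 0.0 | 1.8 | 0.8 | 0.7 |
| 0.5 | 2.3 | −1.6 | −0.1 | 1.4 | 1.0 | 0.7 |
| 0.8 | 1.4 | −2.5 | −0.1 | 1.2 | 1.3 | 0.7 |

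At b = 0.8 the raw bias exceeds 0.2 × 4 = 0.8 because the cap flattens the relation between post and pre.

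**Step 4, chance spread at b = 0.2.** With no dose effect, raw mean change differs by 3 or more points between the best and worst dose in about 5%, 13%, 22% and 32% of runs at baseline SD 3, 4, 5 and 6. After adjustment the figure is below 0.1%. Of the slopes tried, 0.2 is the least favourable to raw change; at 0.8 the raw figures are only 0.2% to 5.7%.

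**Step 5, what adjustment leaves behind.** A second set of runs used pre-injection mean 12, SD 5, slope 0.4, residual SD 2.5 and no dose effect. The figures are top minus lowest dose.

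- 4-point imbalance, no complication: raw +2.40, adjusted −0.02.
- 4-point imbalance with a separate ceiling model (both scores built on one underlying score, capped at 24): raw +0.62, adjusted −0.33.
- 4-point imbalance, pre-score reliability 0.8: raw +2.34, adjusted −0.34.
- 2-point cohort drift unrelated to baseline: raw 2.01, adjusted 2.00.
- 4-point imbalance, slope changed to 1, reliability 0.8: raw about 0, adjusted −0.79.

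The last two cases matter most. Adjustment does nothing for drift that the pre-injection score does not capture. It can also create a bias where raw change had none.

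**The case against.** The efficacy objective is preliminary and secondary, there are no hypotheses, and Protocol 10.6 asks for descriptive statistics, which the SAP delivers. A reader might infer that a planned inference is invalid. It is not, because no between-dose inference is planned. A reader might also infer that the SAP breaches Protocol 10.3. It does not, because that passage is permissive.

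The link to dose selection should not be overstated either. Protocol 10.6 names no LVEBD contrast or threshold, LVO and duration are also secondary endpoints, and Protocol 7.3.1 names LVO as the utility. Nothing shows that raw LVEBD change would decide the choice.

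There are partial safeguards. Pre- and post-injection scores and suboptimal-baseline status are tabulated by dose, so an imbalance would be seen. The suboptimal summary partly stratifies on baseline. Blinded reading in random order after all images are obtained limits reader drift aligned with dose. At slope 0.2 the planned post-injection mean is almost as precise as the adjusted contrast (SE 0.77 against 0.71).

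All of this stands, and it limits the point to interpretation and precision. It does not dispose of it. Seeing an imbalance does not tell the reader how much of a dose difference it explains. The subgroup splits cohorts of 12 further. The post-injection mean does well only when the slope is low; at higher slopes it carries the imbalance itself, in the opposite direction.

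**Conclusion.** The point holds as a recommended improvement. Unadjusted LVEBD change by dose, in sequential non-randomised cohorts of 12 on a capped score, can present a baseline difference as a dose difference. Under the assumed inputs (baseline SD 5, slope 0.2 to 0.8, residual SD 2), a 4-point imbalance produces a spurious difference of about 3.2 to 1.4 points in raw change and about 0.1 or less after adjustment. The SE of a dose difference falls from about 1.8-1.2 to about 0.7. None of these inputs is in the documents, so the direction is secure and the size is not.

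The tempting stronger claim is that adjusting for the pre-injection score removes the confounding. The design does not support it. Site, operator, calendar-time and case-mix differences between cohorts remain, and a ceiling or measurement error in the pre-score can leave or add bias, by 0.3 to 0.8 points in the cases tried.

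**What to change.** Keep every raw table and figure in SAP 5.4.1.2. Add one linear model, labelled exploratory, on the FAS and PP sets: LVEBD change (or post-injection score, which gives the same dose contrasts) on dose at three levels, with the pre-injection score as covariate. Report the adjusted mean per dose and the differences from 2.5 µl/kg with 95% CIs, and check the linear fit to a bounded score by residuals or a bootstrap interval. Name which pre-injection imaging mode supplies the covariate, since Protocol 7.1.1 acquires two and the SAP does not say which one is scored.

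Add a sentence saying that the model reduces baseline confounding but cannot address other differences between cohorts, and that raw and adjusted results are to be read together.

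Do not use the model to predict change at a low total score as support for the suboptimal-baseline endpoint. That subgroup is defined by contiguous non-visualised segments within a view, not by total score.

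The cost is one SAP paragraph and one table per analysis set. No new data are needed, and Protocol 10.3 already allows for an exploratory analysis of this kind.
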